#### **2.6.2 NYHA class change**

The heart failure symptoms and the NYHA class will be recorded on the CRF page: “Signs and Symptoms of Heart Failure including New York Heart Association Classification”.

[Table 2-8](#) defines the NYHA class change at each post-baseline visit.

**Table 2-8 NYHA Class Change**

NYHA Class Change		Post-Baseline Visit				
		Class I	Class II	Class III	Class IV	Death
Baseline	Class I	unchanged	worsened	worsened	worsened	worsened
	Class II	improved	unchanged	worsened	worsened	worsened
	Class III	improved	improved	unchanged	worsened	worsened
	Class IV	improved	improved	improved	unchanged	worsened

For patients who died, the NYHA class will be set to a fifth category (death), and the NYHA class change after the death will be categorized into “worsened”. For patients who permanently discontinue study treatment, values collected after permanent discontinuation will generally be included in the analysis.

The NYHA class change will be analyzed using a longitudinal proportional cumulative odds model, in which, the response variable will be the NYHA class change (order defined by “improved” < “unchanged” < “worsened”); stratum (ACEi, ARB, No RASi), region, treatment (LCZ696, IMT), visit, treatment-by-visit interaction, baseline NYHA class, stratum-by-baseline and visit-by-baseline interactions will be included as fixed-effect factors; BSBP and stratum-by-BSBP interaction will be included as covariates; patient-specific intercepts will be included as random effects. The analysis will include all post-baseline scheduled visits up to Week 24 (Week 2, Week 4, Week 8, Week 12, Week 16, Week 20 and Week 24) and will be performed based on the likelihood method with an assumption of MAR for missing data (other than due to death).

Based on the longitudinal proportional cumulative odds model, the secondary null hypothesis, H4, will be tested based on the testing strategy (if applicable), the estimate and the two-sided 95% confidence interval will be provided for the adjusted odds ratio (LCZ696 / IMT) at each post-baseline scheduled visit (Week 2, Week 4, Week 8, Week 12, Week 16, Week 20 and Week 24). The corresponding one-sided p-values will also be provided based on the model.

In addition, the improvement and the deterioration in NYHA class will be analyzed separately using longitudinal binary logistic regression models, in which, the response variables will be, accordingly, the NYHA class improvement (event defined by NYHA class change of level “improved”) and the NYHA class deterioration (event defined by NYHA class change of level “worsened”); stratum (ACEi, ARB, No RASi), region, treatment (LCZ696, IMT), visit, treatment-by-visit interaction, baseline NYHA class, stratum-by-baseline and visit-by-baseline interactions will be included as fixed-effect factors; BSBP and stratum-by-BSBP interaction will be included as covariates; patient-specific intercepts will be included as random effects. The analysis will include all post-baseline scheduled visits up to Week 24 (Week 2, Week 4, Week 8, Week 12, Week 16, Week 20 and Week 24) and will be performed based on the likelihood method with an assumption of MAR for missing data (other than due to death).

Based on the longitudinal binary logistic regression models, the estimates and the two-sided 95% confidence intervals will be provided for the adjusted odds ratios (LCZ696 / IMT) at each post-baseline scheduled visit (Week 2, Week 4, Week 8, Week 12, Week 16, Week 20 and Week 24). The one-sided p-values will also be provided based on the longitudinal binary logistic model.

Besides, the NYHA class and the NYHA class change will be summarized by treatment group and visit, for overall and for each stratum (ACEi, ARB, No RASi), using the numbers and percentages of patients within each category.

The heart failure symptoms will be summarized by treatment group and visit, for overall and for each stratum (ACEi, ARB, No RASi), using the numbers and percentages of patients with each heart failure symptom.

As additional supportive analyses, the Mantel-Haenszel estimates and the corresponding 95% confidence intervals will be provided by visit, for the relative risks and the risk differences, for NYHA improvement and NYHA deterioration, accordingly.

The FAS will be used for the above analyses.

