9.4.2 Statistical model, hypothesis, and method of analysis

Testing strategy

The following primary null hypotheses will be included in the testing strategy.

- H_1 : LCZ696 is no better than the comparator in change from baseline in log(NT-proBNP) at Week 12 in the overall study population
- H_2 : LCZ696 is no better than the comparator in change from baseline in 6MWD at Week 24 in patients with B6MWD ranging from 100 meters to 450 meters.

The following secondary null hypotheses will be included in the testing strategy.

- H_3 : LCZ696 is no better than the comparator in change from baseline in KCCQ CSS at Week 24 in the overall study population.
- H_4 : LCZ696 is no better than the comparator in NYHA change from baseline at Week 24 in the overall study population.

Each null hypothesis is tested against the one-sided alternative that LCZ696 is better than the comparator in the corresponding variable.

In order to control the family-wise type-I error rate at the one-sided 0.025 significance level, a sequentially rejective multiple testing procedure based on the graphical presentation ([Bretz et al 2009](#)) will be employed, whereby H_1 and H_2 will be tested first at initially assigned level of one-sided $(9/10) \times \alpha = 0.0225$ and one-sided $(1/10) \times \alpha = 0.0025$, accordingly. If H_1 and/or H_2 are rejected, the alpha for the rejected null hypotheses will be propagated to H_3 , such that, H_3

[figure not shown]
will be tested at the updated alpha level (one-sided 0.025 if both H_1 and H_2 are rejected; one-sided 0.0225 if H_1 is rejected but H_2 is not rejected; one-sided 0.0025 if H_2 is rejected but H_1 is not rejected); if H_3 is rejected, the alpha will be propagated to H_2 or H_4 based on the initial step rejection status.

- With H_1 rejected but H_2 not rejected at the initial step, if H_3 is rejected at one-sided 0.0225, the alpha will be propagated to H_2 , such that, H_2 will be tested again at one-sided 0.025; if H_2 is rejected at one-sided 0.025, the alpha will be further propagated to H_4 . Otherwise, the testing procedure will stop.
- With H_2 rejected but H_1 not rejected at the initial step, if H_3 is rejected at one-sided 0.0025, the alpha will be propagated to H_4 , such that, H_4 will be tested at one-sided 0.0025. Otherwise, the testing procedure will stop.

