**Figure 1-1 Study design**

Screening	Stratified Randomization	Double-Blind Treatment	
Up to 2 weeks	Visit 101	24 weeks	
		Titration	Maintenance
		1-4 weeks	20-23 weeks

Approximately 2500 patients will be randomized in this study.

Patients will be initially stratified into one of three strata according to prior renin-angiotensin system inhibitor (RASi) treatment for comorbidities: angiotensin converting enzyme inhibitor (ACEi), angiotensin receptor blocker (ARB) or no RASi. Patients will then be randomized at a 1:1 ratio to receive either LCZ696 or comparator (i.e., IMT). Patients in the ACEi stratum will be randomized to receive either LCZ696 or enalapril. Patients in the ARB stratum will be randomized to receive either LCZ696 or valsartan. Patients in the no RASi stratum will be randomized to receive either LCZ696 or placebo. Patients in the ACEi and ARB strata must have a history of hypertension (HTN). There will be no designated proportion of patients in

each stratum, the strata will populate based upon the patient's prior treatment regimen. In addition, randomization will be stratified by region.

For the purpose of blinding, the corresponding placebos are also dispensed to the patients. [Table 1-1](#) summarizes the study medications for each treatment group and each stratum (ACEi, ARB, No RASi).

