- With H2 rejected but H1 not rejected at the initial step, if H3 is rejected at one-sided 0.0025, the alpha will be propagated to H4, such that, H4 will be tested at one-sided 0.0025. Otherwise, the testing procedure will stop.
- With both H1 and H2 rejected at the initial step, if H3 is rejected at one-sided 0.025, the alpha will be propagated to H4, such that, H4 will be tested at full alpha (one-sided 0.025). Otherwise, the testing procedure will stop.

Figure 2-1 provides graphical illustration of the sequentially rejective testing procedure.

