### 3 Sample size calculation

The sample size (2500 randomized patients) has been chosen in order to provide adequate power to evaluate both primary and secondary endpoints.

With an alpha of one-sided 0.0225, the power for the NT-proBNP will range from 92% to more than 99%, to detect a relative reduction ranging from 11% to 24% in change from baseline to Week 12 in NT-proBNP, assuming a standard deviation of 0.81 for change from baseline in the log-transformed NT-proBNP (based on PARAMOUNT-HF data of patients with baseline KCCQ CSS < 75) and an overall drop-out rate of 10%.

With an alpha of one-sided 0.0025, the power for the 6MWD will range from 90% to 99%, to detect a mean difference ranging from 22 meters to 30 meters in change from baseline to Week 24 in 6MWD, assuming a standard deviation of 120 meters ([Ingle et al 2005](#)), an overall drop-out rate of 10%, and an overall proportion of 88% for patients with B6MWD ranging from 100 meters to 450 meters.

With an alpha of one-sided 0.0225, the power for the KCCQ CSS will range from 87% to 99%, to detect a mean difference ranging from 2 points to 3 points in change from baseline to Week 24 in KCCQ CSS, assuming a standard deviation of 15.52 points for change from baseline in the KCCQ CSS (based on PARAMOUNT-HF data of patients with baseline KCCQ CSS < 75) and an overall drop-out rate of 5%.

All alpha levels in the following sample size calculations will be one-sided 0.025.

This sample size of 2500 randomized patients aims to provide a power of approximately 90%, with the one-sided alpha level of 0.025, to demonstrate a 5% responder advantage in at least 5-point deterioration for patients who are treated with LCZ696 over IMT when assuming the proportion of patients with at least 5-point deterioration from baseline to Week 24 in the IMT group is 20% (based on PARAMOUNT-HF data of patients with baseline KCCQ CSS < 75) and an overall 5% dropouts.

With the same assumption of the dropout rate, this sample size will also provide a power of 69% to detect a 5% responder advantage in at least 5-points improvement in the KCCQ clinical summary score for patients who are treated with LCZ696 over IMT when assuming the proportion of patients with at least 5-points improvement from baseline to Week 24 in the IMT group is 55% (based on PARAMOUNT-HF data of patients with baseline KCCQ CSS < 75).

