**Table 3-2 Sensitivity of power for at least 5-points improvement in KCCQ CSS to changes in assumptions for N = 2500**

Assumed probability of at least 5-points improvement			Power for at least 5-points improvement (one-sided alpha = 0.025)			
IMT	LCZ696	Difference (LCZ696 - IMT)	With 5% drop-out rate	With 10% drop-out rate	With 15% drop-out rate	With 20% drop-out rate
55%	60%	5%	69%	67%	65%	62%
41%	46%	5%	69%	67%	64%	62%

The assumed dropout rates ([Table 3-1](#) and [Table 3-2](#)) are for the purpose of power sensitivity analysis. During the conduct of the study, all efforts will be made to reduce missing data.

For other secondary endpoints, this sample size will provide adequate powers for reasonable effect size assumptions: power of 90% for NYHA class change, assuming 14% of the patients in the comparator and 19% of the patients in the LCZ696 group are improved in NYHA class change, 6% of the patients in the comparator and 5% of the patients in the LCZ696 group are worsened in NYHA class change (based on Week 24 PARAMOUNT-HF data of patients with baseline KCCQ CSS < 75); and power of approximately 90% to detect a between treatment group mean difference of 1.4 points or more in change from baseline in SF-36 physical component summary score, assuming a standard deviation of 10-points ([Edelmann et al 2013](#)).

East 6.3 was used for the sample size calculations.

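### The NYHA test (H4) assumes a constant gap between its two cut-points over Weeks 2 to 24; if more patients change class as the trial goes on, its Week 24 standard error is too small and the nominal 0.025 test runs at about 0.03 to 0.06

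*SAP*

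**What the plan says.** SAP 2.6.2 and Protocol 9.5.1.3 define NYHA change as improved, unchanged or worsened relative to baseline, with death counted as worsened. For the test: "The NYHA class change will be analyzed using a longitudinal proportional cumulative odds model". Visit, treatment-by-visit, baseline class, stratum-by-baseline and visit-by-baseline enter as fixed effects, and baseline systolic pressure and its stratum interaction as covariates. The only random effect is a patient intercept. All seven visits from Week 2 to Week 24 are used, the fit is by likelihood, and no empirical variance is mentioned. The non-convergence rule in SAP 2.1.1 only removes terms.

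The Protocol 9.4.2 testing strategy is adopted "In order to control the family-wise type-I error rate at the one-sided 0.025 significance level". If H1, H2 and H3 are all rejected, H4 "will be tested at full alpha (one-sided 0.025"). If H1 is not rejected but H2 and H3 are, H4 "will be tested at one-sided 0.0025".

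For power, SAP section 3 assumes that 14% (comparator) and 19% (LCZ696) improve, and that "6% of the patients in the comparator and 5% of the patients in the LCZ696 group are worsened in NYHA class change". It states 90% power. These are Week 24 figures; none are given for earlier visits.

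**The concern.** Write the model as logit P(Y ≤ k) = θ_k − (visit + baseline + treatment-by-visit + … + patient intercept), k = 1, 2. Every term in the bracket shifts both cut-points equally, so θ_2 − θ_1 is one number for all seven visits. The model can describe patients drifting towards improvement or worsening. It cannot describe both outer categories growing at the same time.

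Several design features point to growth:
- Everyone is unchanged at randomization by construction.
- A death is worsened at every later visit, so that part can only accumulate.
- Week 2 lies inside the 1 to 4 week titration period (Protocol 3.1).
- Background therapy is to be optimized throughout (Protocol 3.4).

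If spread grows, the fitted gap is a compromise over visits. It predicts fewer movers at Week 24 than there are, so Week 24 outcomes vary more than the model expects and its standard error is too small.

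H4 is the only confirmatory test with this restriction. H1 to H3 use repeated-measures models with unstructured covariance as the primary specification, so their residual spread may differ by visit. At stake are the error rate of a confirmatory hypothesis and the coverage of the Week 24 odds-ratio interval.

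**Working it through.** **1. The plan's power figure.** Inputs: "The sample size (2500 randomized patients) has been chosen"; patients are "randomized at a 1:1 ratio to receive either LCZ696 or comparator"; and "All alpha levels in the following sample size calculations will be one-sided 0.025". Category shares (improved/unchanged/worsened) are 19/76/5 against 14/80/6.

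Wilcoxon form with ties:
- P(LCZ696 better) = 0.19 × 0.86 + 0.76 × 0.06 = 0.2090.
- P(LCZ696 worse) = 0.14 × 0.81 + 0.80 × 0.05 = 0.1534.
- Half the difference = 0.0278.
- Null variance = (2/1250)/12 × (1 − 0.165³ − 0.78³ − 0.055³) = 0.0016/12 × 0.5208 = 6.94 × 10⁻⁵, so SE = 0.00833.
- Power = Φ(0.0278/0.00833 − 1.96) = Φ(1.38) = 91.6%. With 5% dropout (N = 2375) it is 90.2%.

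The stated 90% is reproduced. It comes from a Week 24 comparison and does not depend on common cut-points.

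**2. Can one gap fit all visits?** Marginal gap = logit(1 − worsened) − logit(improved), scaling both outer categories down together:

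| Unchanged | Improved / worsened | Gap |
|---|---|---|
| 80% (Week 24, plan) | 14% / 6% | 2.75 + 1.82 = 4.57 |
| 85% | 10.5% / 4.5% | 3.06 + 2.14 = 5.20 |
| 90% | 7% / 3% | 3.48 + 2.59 = 6.06 |
| 95% | 3.5% / 1.5% | 4.18 + 3.32 = 7.50 |

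A location shift leaves the gap unchanged, so no visit effect can turn 6.06 into 4.57.

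**3. Size of the Week 24 test.** The model was fitted by maximum likelihood with quadrature to null data. Both arms have 14/80/6 at Week 24; the Week 2 share unchanged is assumed. With r = model SE / sandwich SE, the size is 1 − Φ(1.96 r). The worked case has 70% class II and 30% class III at baseline, constant latent correlation 0.8 and linear growth. The range covers linear or square-root growth, constant (0.6 or 0.8) or decaying correlation, and one or two baseline classes.

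| Unchanged at Week 2 | r | 1.96 r | Size | Range |
|---|---|---|---|---|
| 80% (no growth) | 1.000 | 1.960 | 0.025 | 0.025–0.027 |
| 85% | 0.928 | 1.819 | 0.034 | 0.032–0.036 |
| 90% | 0.853 | 1.672 | 0.047 | 0.040–0.049 |
| 95% | 0.776 | 1.521 | 0.064 | 0.051–0.065 |

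Other shapes:
- Spread complete by Week 8: 0.033–0.040.
- Only improvement grows (7% to 14%): 0.037–0.038.
- Only worsening grows (3% to 6%): 0.034–0.036.
- Improvement grows while worsening falls from 9% to 6%: 0.030–0.032.

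At the 0.0025 level the size is 0.004–0.015 when both categories grow and 0.0025–0.0028 when they do not.

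**4. Simulated trials, N = 2500, 600 per scenario (Monte Carlo SE about 0.005).**

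| Unchanged at Week 2 | Growth, correlation | Model SE | Sandwich SE |
|---|---|---|---|
| 80% | none, constant | 0.023 | 0.024 |
| 90% | linear, constant | 0.052 | 0.023 |
| 90% | square-root, decaying | 0.046 | 0.028 |
| 85% | linear, decaying | 0.037 | 0.028 |

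**5. Visit-specific cut-points.** The large-sample size returns to 0.025–0.027 in every case tried. A short simulation (300 trials) gave 0.037 with either standard error. Its Monte Carlo SE is √(0.05 × 0.95/4/300) = 0.006, so this lies a little under 2 SE above 0.025. A longer repeat with 90% unchanged at Week 2 fell within Monte Carlo error of 0.025.

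**The case against.** The strongest reply is that growth is assumed. The documents give NYHA change only at Week 24. Protocol 6.6.1.1 describes the classification as subjective and liable to change often, and the first modelled visit is Week 2, not randomization. Reclassification noise, together with the switch from prior therapy at randomization, could already have produced most of the spread by then. No death rate is given, so the contribution of deaths is unknown. All of this stands. A reader might infer that spread must grow, or that the test runs at 0.04 to 0.05. The documents support neither: that size needs about 90% unchanged at Week 2 with growth afterwards, and no such figure appears.

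The reach is also limited. Every path to H4 requires both H2 and H3 to be rejected. The tests of H1 to H3 are untouched. The separate binary improvement and deterioration models have one cut-point each with free visit effects, so this mechanism does not reach them. They and the by-visit tables would show a changing spread, but they do not set the H4 p-value. The plan also powers the route to H4 (92% or more for H1, 90% to 99% for H2, 87% to 99% for H3, under its own assumptions), so H4 cannot be dismissed as unlikely to be tested.

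A reader might also infer that the NYHA imputation models share the fault. They do not: SAP 2.6.4 fits a separate cumulative odds model at each visit, so the cut-points there already vary.

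**Conclusion.** The concern holds conditionally. As written, the H4 model fixes the gap between cut-points over time and relies on model-based standard errors. If the share of patients who have changed class grows between Week 2 and Week 24, the nominal one-sided 0.025 test runs at about 0.03 to 0.06, and the 95% interval for the Week 24 odds ratio is too narrow. If spread is complete at Week 2 and within-patient correlation is roughly constant, the size is about nominal. Every growth shape tried was anti-conservative. The Week 24 effect estimate is not biased under the null.

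The figures rest on the plan's comparator rates at Week 24 and on assumed Week 2 shares (85% to 95% unchanged), a Gaussian latent correlation, an assumed class II/III mix (70/30 or 60/40), and no missing data. Region, stratum and systolic pressure terms were left out. The plan claims error control for this hypothesis, so the point should be fixed. It is confined to the last hypothesis in the graph and does not undermine the primary analyses.

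**What to change.** Before unblinding, amend SAP 2.6.2 and align Protocol 9.5.1.3, or record the change in SAP section 4, in one or both of these ways:
- Base the H4 p-value and confidence interval on the empirical (sandwich) standard error, clustered by patient.
- Let both cut-points vary by visit, keeping treatment proportional within each visit.

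Either alone restored the level in the scenarios tried. Apply the same choice to the NYHA subgroup model (SAP 2.6.5) and to the analysis of the multiply imputed data (SAP 2.6.4). The imputation models need no change.

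The cost is SAP wording, a slightly wider interval and a few nuisance parameters: 14 cut-points in place of 2 cut-points plus 6 visit shifts, so 14 − 8 = 6 more in 2500 patients.

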### **2.6.3 Short Form Health Survey (SF-36)**

The SF-36 consists of 36 individual items comprising eight scales: physical functioning, role-physical, bodily pain, general health, vitality, social functioning, role-emotional and mental health. For each of the eight scales, a raw score ranging from 0 to 100, and a normalized score (normed to the US population) will be calculated. Based on the normalized scores, two overall summary scores: physical component summary (PCS) score and mental component summary (MCS) score will be calculated. The raw scores, the normalized scores and the overall summary scores will be provided by Optum.

The raw scores, the normalized scores and the overall summary scores will be summarized by treatment group and visit, accordingly, for overall and for each stratum (ACEi, ARB, No RASi), using number of observations, mean, standard deviation, median, minimum, Q1, Q3, and maximum.

#### **2.6.3.1 SF-36 physical component summary (PCS) score**

For patients who have died, the SF-36 PCS score after the death will be imputed as zero. For patients who permanently discontinue from study treatment, values collected after permanent discontinuation will generally be included in the analysis.

The changes from baseline in SF-36 PCS score will be analyzed using a MMRM model, in which, the response variable will be the changes from baseline in SF-36 PCS score; stratum (ACEi, ARB, No RASi), region, treatment (LCZ696, IMT), visit and treatment-by-visit interaction will be included as fixed-effect factors; baseline SF-36 PCS score (BPSS), BSBP, stratum-by-BPSS, stratum-by-BSBP and visit-by-BPSS interactions will be included as covariates; the within-patient covariance will be modeled using an unstructured covariance matrix (a common matrix for the two treatment groups). The analysis will include all post-baseline scheduled visits up to Week 24 (Week 16 and Week 24) and will be performed based on the likelihood method with an assumption of MAR for missing data (other than due to death).

Based on the MMRM model, the estimates and the two-sided 95% confidence intervals will be provided for the adjusted mean SF-36 PCS scores and the adjusted mean changes from baseline in the SF-36 PCS score at each post-baseline scheduled visit (Week 16 and Week 24) in both treatment groups (LCZ696 and IMT), and for the adjusted mean difference (LCZ696 minus

IMT) at each post-baseline scheduled visit (Week 16 and Week 24). The one-sided p-values will also be provided based on the MMRM model.

In addition, the improvement and the deterioration in SF-36 PCS score will be analyzed separately using longitudinal binary logistic regression models, in which, the response variables will be, the SF-36 PCS score improvement (event defined by at least 3.4 points improvement in SF-36 PCS score) and the SF-36 PCS deterioration (event defined by at least 3.4 points deterioration in SF-36 PCS score), accordingly; stratum (ACEi, ARB, No RASi), region, treatment (LCZ696, IMT), visit and treatment-by-visit interaction will be included as fixed-effect factors; BPSS, BSBP, stratum-by-BPSS, stratum-by-BSBP and visit-by-BPSS interactions will be included as covariates; patient-specific intercepts will be included as random effects. The analysis will include all post-baseline scheduled visits up to Week 24 (Week 16 and Week 24) and will be performed based on the likelihood method with an assumption of MAR for missing data (other than due to death).

Based on the longitudinal binary logistic regression models, the estimates and the two-sided 95% confidence intervals will be provided for the adjusted odds ratios (LCZ696 / IMT) at each post-baseline scheduled visit (Week 16 and Week 24). The corresponding one-sided p-values will also be provided based on the longitudinal binary logistic model.

As additional supportive analyses, the Mantel-Haenszel estimates and the corresponding 95% confidence intervals will be provided by visit, for the relative risks and the risk differences, for SF-36 PCS score improvement and SF-36 PCS score deterioration, accordingly.

The FAS will be used for the above analyses.

